3.4 Primary Study Endpoints

Patient: Completion of all imaging examinations with laboratory results.

Data analysis:

Objective 1: Descriptive study. With biopsy and/or surgical histopathology as gold standard, the sensitivity, specificity and accuracy of PET/MR will be calculated.

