1.5 Risks and Benefits

C-11 choline is involved in phosphorylation process integrated into phospholipids in the cell membrane as part of phosphatidylcholine, which is vital in prostate cancer cell. The main risk involves the exposure to the radioactivity associated with the C-11 isotope incorporation. This exposure has been calculated to be much lower than the F-18 FDG. In addition, there is no radiation risk related to MR scan. For MR safety concern, each subject will undergo MR safety screening performed by PET/MR technologist prior to imaging.

2 Study Objectives

Primary Objective:

- 1) Test whether a hybrid combination of focused C-11 choline PET/MR and pelvic mpMRI on a PET/MR system is feasible

Secondary Objective(s):

- 1) Determine the efficacy (added values) of a hybrid combination of molecular focused C-11 choline PET/MR and functional and anatomic pelvic mpMRI in comparison with clinical findings.
- 2) Determine the efficacy (added values) of a torso C-11 choline PET/MR in comparison with conventional CT and bone scan in depicting metastasis to lymph node and bone.

3 Study Design

This study will be a prospective study to test and optimize the feasibility of hybrid 3T PET/MR scan in diagnosing and staging high and very high risk prostate cancer patients.

The FDA approved C-11 choline PET tracer at a dose of 12-14 mCi will be administered intravenously prior to fused PET/MR scan, and prior to diagnostic pelvic mpMRI scan while patient lying in the scanner.

In addition, single dose of Gadavist® (Gadobutrol, Bayer) is at no more than 0.1 mmol/kg will be administered intravenously for pelvic mpMRI.

The whole imaging procedure will be conducted on an FDA approved GE SIGNA 3T PET/MR scanner.

The C11-choline PET/MR and pelvic mpMRI findings and results will be compared with serum PSA level, Gleason score, clinical CT and nuclear medicine whole body bone scintigraphy findings, and histopathological results obtained through standard of care management.

Our primary interest is to investigate the feasibility of hybrid C11-Choline PET/MR fusion and pelvic mpMRI in imaging primary prostate cancer.

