Acquisition time per table bed	Part 1: Torso C-11 choline PET/MR				Part 2: Hybrid dedicated focused C-11 choline PET/MR and pelvic mpMRI			
2-5 min/bed	PET		AC	Diagnostic MR pulse sequences				
2-5 min/bed	PET		AC	Diagnostic MR pulse sequences				
2-5 min/bed	PET		AC	Diagnostic MR pulse sequences				
2-5 min/bed	PET		AC	Diagnostic MR pulse sequences				
2-5 min/bed	PET		AC	Diagnostic MR pulse sequences				
2-5 min/bed	PET				Focused C-11 choline PET/MR 		Pelvic mpMRI (anatomic and functional sequences) without e-coil	
Time	25-30 min				45-50 min			

AC=attenuation correction

mpMRI = multiparametric MRI

e-coil = endorectal coil (for illustration purpose only, will not be used in current study)

* = F-18 FDG PET/MR shown for illustration purpose

** = C-11 choline PET/CT shown for illustration purpose

*** = T2W shown for illustration purpose

Figure 2. Workflow of Readout Sessions (parts 1-3)

[figure not shown]

Table 1. Summary of imaging finding evaluation

	C-11 choline PET/MR (research)	Clinical imaging exams	Reference standard	Findings
Local T staging: Prostate	Focused pelvic C-11 choline PET/MR	Pelvic mpMRI	Pathology results (biopsy, surgery if available)	Localization Characterization Local tumor (T) staging
Metastasis to pelvic lymph nodes(N)				
Pelvis	Focused C-11 choline PET/MR	Pelvic mpMRI CT	Pathology results (biopsy, surgery if available)	Localization SUV values
Torso	Torso C-11 choline PET/MR	CT	Pathology results (biopsy, surgery if available)	Localization SUV values
Metastasis to pelvic bone (M)				
Pelvis	Torso and focused C-11 choline PET/MR	Pelvic mpMRI CT Bone scan	Pathology results (biopsy, surgery if available)	Localization SUV values
Extra-pelvis	Torso C-11 choline PET/MR	CT Bone scan	Pathology results (biopsy, surgery if available)	Localization SUV values
Visceral metastasis (M)				
Visceral metastasis (M)	Torso C-11 choline PET/MR	CT	Pathology results (biopsy, surgery if available)	Localization SUV values

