4.2 Exclusion Criteria

- Patients who already received primary treatment or neo-adjuvant therapy.
- Patients who refuse undergoing routine clinical imaging (i.e., pelvic mpMRI, CT, bone scan) for staging. Reimbursement of pelvic mpMRI may be provided. CT and bone scan may be done elsewhere outside of Mayo Clinic but should be of diagnostic quality. Research C-11 choline PET/MR will not substitute pelvic mpMRI, CT, or bone scan in this study.
- Patients cannot tolerate MRI (e.g., claustrophobia, severe back pain or spasm, involuntary movement [e.g., tremor, dystonia]).
- Patients have total hip arthroplasty (THA), which can cause substantial susceptibility artifact and degrade image quality of mpMRI.
- Patients have cardiac pacemaker, cochlear implants, neurostimulator, medical device which is unsafe at 3 Tesla, or foreign metallic body in the eyes or orbit.
- Patients have contraindication to gadolinium based MR contrast agents (e.g., renal failure, severe reaction to gadolinium based MR contrast agents). eGFR should be above 30 within 30 days the time of mpMRI.

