5.9.4 Return or Destruction of Study Drug

After injection of the C 11 choline the syringe will be assayed for residual radioactivity, to be used in calculation of the precise injected dose. The syringe will then disposed of in the radioactive container for 3-4 hours, about ten half-life durations of C11-Choline (C11-Choline half-life of 20 minutes).

6 Study Procedures

Patients who have completed or will complete diagnostic body CT scan and nuclear medicine bone scan as part of standard care will be recruited and consented for participation in the study

PET/MRI is preferably scheduled 6 weeks after prostate biopsy to minimize the effects of post biopsy hemorrhage.

6.1 Day 0

Informed consent discussion with subject by research coordinator. Consent form signed by subject. Medical records will be reviewed by study coordinator. Subject's eGFR will be determined. If current serum creatinine level is unavailable, labs will be obtained for review.

Subject will be reminded to drink 48 ounces of water the day prior to study procedures. On the morning of the procedure, subjects will be counseled to fast for four hours prior to the procedure and drink 24 ounces of water.

6.2 Day 1

The patient will be screened for MR safety prior to entering the scan room, which may include the use of ferromagnetic screening.

[figure not shown]
1. Vital signs (sitting blood pressure, heart rate, respiratory rate, temperature) are measured by the radiology nurse, who records the results on the source document.
2. Investigator MD or research coordinator to see patient, review vital signs and discuss study objectives, explain the imaging procedures, answer questions. MD will sign and date the source document.
3. Subject is brought to the PET/MR imaging suite. Total dose of 12-14 mCi C-11 choline is injected I.V.
4. Torso PET/MR fusion scan is completed. Imaging time 20-30 minutes.
5. Pelvic mpMRI with PET data of pelvis completed. Imaging time 40-45.
6. Following completion of imaging, subject will return to the relax room and vital signs (sitting blood pressure, heart rate, respiratory rate and temperature) will be re-checked by

the radiology nurse, with the study coordinator recording the data in the source documents.

7. Subject will be discharged.

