7.2 Statistical Methods

Descriptive Statistics

Descriptive statistics will be used to describe the average time of the total procedure, patients' tolerance and satisfaction level about the procedure. Paired t-test will be used to compare the suspicious lymph nodes and suspicious osseous lesions in the pelvis and extrapelvic regions detected by hybrid C11-choline PET/MR and pelvic multiparametric MRI method and by conventional CT and bone scan to investigate if the new method is able to detect more lymph nodes and osseous lesions compared to the conventional method. Paired t-test will also be used to compare the average SUV of lymph nodes and osseous lesions in the pelvis and extrapelvic regions by new method with that by conventional method to investigate if the new method provided more clarity in terms detecting the lymph nodes and lesions compared to the old method. If the patients' biopsy and surgery results available, sensitivity, specificity, positive predictive value and negative predictive value of detecting malignant lymph nodes and osseous lesions by the new method and by conventional method will be estimated and compared using McNemar's test.

Handling of Missing Data

As the sample size is 20 and imaging is completed over one day, no missing imaging data is anticipated.

Multiplicity

In current project, there is one primary objective and we don't have to adjust for multiple comparison.

Interim Analysis

There will not be interim analysis for the study.

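### Per-patient feasibility is bare completion among replaced, completers-only subjects; no rule records whether the hybrid images, above all the focused pelvic PET, were usable

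*Combined protocol and SAP*

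**What the plan says.** Section 2 states the primary objective: "Test whether a hybrid combination of focused C-11 choline PET/MR and pelvic mpMRI on a PET/MR system is feasible". Section 3.4 then sets the patient-level primary endpoint: "Patient: Completion of all imaging examinations with laboratory results". Under Objective 1 the same section adds: "With biopsy and/or surgical histopathology as gold standard, the sensitivity, specificity and accuracy of PET/MR will be calculated".

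The only other feasibility measures are in 7.2: "Descriptive statistics will be used to describe the average time of the total procedure, patients' tolerance and satisfaction level about the procedure". On missing data, 7.2 says that "no missing imaging data is anticipated". It has no rule for a scan that was acquired but cannot be interpreted.

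Image quality is mentioned elsewhere, but not as an outcome. For comparator scans, 4.2 says "CT and bone scan may be done elsewhere outside of Mayo Clinic but should be of diagnostic quality". Section 3.3 uses the term diagnostic quality for one MR sequence. The reading lists in 3.3 cover lesions, staging, nodes, bone and, where possible, SUV; no item asks whether a component was readable.

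Section 3.2 wants twenty subjects to complete. Under 4.4, a subject who cannot finish because of claustrophobia is withdrawn, and early withdrawals are replaced. The only analysis population in 7.3 is subjects who completed all procedures and follow-up.

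**The concern.** A feasibility endpoint should be able to register the ways in which a technique can fail. Here a subject may fail to finish the session, or may finish it and yield images that cannot be used. The first kind of failure is largely removed by withdrawal, replacement and a completers-only population. The second is not recorded in any text that can be read.

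The component most exposed is the one that makes the scan hybrid. In Figure 1, "Hybrid dedicated focused C-11 choline PET/MR and pelvic mpMRI" is Part 2, acquired after the torso scan, with a tracer whose stated half-life is 20 minutes and a subject who must lie still for a further 40 to 50 minutes. At stake is what the headline result means: 20 of 20 completed could be reported without saying whether the focused PET was interpretable.

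**Working it through.** **1. Plan figures.** The plan gives no feasibility rate, target or threshold, so there is none to reproduce. Its one calculated design figure, 82% power in 7.1, concerns nodal accuracy. With n = 20, d = 0.30, ψ = 0.31 and z = 1.96, the Miettinen approximation Φ[(d√(nψ) − zψ)/√(ψ² − d²(3+ψ)/4)] gives Φ(0.1394/0.1471) = 82.8%. Nothing below depends on it.

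**2. Where an unreadable focused PET would show.**
- Completion (3.4): it would not; the subject counts as complete.
- Time, tolerance, satisfaction (7.2): it would not.
- Accuracy (3.4, 7.2): possibly, but with no handling rule it may be scored negative and appear as low sensitivity. The 7.2 comparisons for nodes and bone treat PET/MR plus mpMRI as one method, and the 3.3 reading list takes torso and focused PET/MR together. Part 1 also covers the pelvis. Readable mpMRI or torso PET could therefore hide the failure.
- Local T staging (Table 1): here focused PET/MR is listed alone, so failure is more visible, but still without a field that separates unreadable from negative.

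**3. Completion by construction.** If k subjects start, do not finish and are replaced, completion among starters is 20/(20 + k). Among completers it is 20/20 = 100% whatever k is.

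**4. Size, with assumed counts** (Clopper-Pearson 95% intervals). Completion of 20/20 reads 100% (83% to 100%) however many focused PETs are readable. Requiring readability gives:
- 16/20 = 80% (56% to 94%)
- 15/20 = 75% (51% to 91%)
- 10/20 = 50% (27% to 73%)

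**5. Is the late PET count-poor?** Inputs: "C11-Choline half-life of 20 minutes" (5.9.4); imaging starts immediately after injection (3.3); Part 1 lasts 25-30 min (3.3, Figure 1) or 20-30 min (6.2); Part 2 lasts 45-50 min (Figure 1), 40-50 min (3.3) or 40-45 min (6.2). The session therefore ends between 60 min (20 + 40, from 6.2) and 80 min (3.3, Figure 1).

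Remaining activity is A(t) = 2^(−t/20):
- Start of Part 2: A(20) = 50%, A(25) = 42%, A(30) = 35%.
- End of session: A(60) = 12.5%, A(75) = 7.4%, A(80) = 6.25%.

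Image counts follow activity summed over the acquisition, N(a,b) = (20/ln 2)[A(a) − A(b)], with 20/ln 2 = 28.85, in minutes at injected activity:
- Part 2, 25-75 min: 28.85 × (0.4204 − 0.0743) = 10.0
- Part 2, 30-80 min: 28.85 × (0.3536 − 0.0625) = 8.4
- First Part 1 bed, 2 min: 28.85 × (1 − 0.9330) = 1.9
- First Part 1 bed, 5 min: 28.85 × (1 − 0.8409) = 4.6

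If emission is collected throughout Part 2, the focused PET gathers about twice the decays of the longest first bed (8.4/4.6 = 1.8; 10.0/4.6 = 2.2). If it occupies one 2-5 min bed, as the Figure 1 row can be read, a 5-min bed at 25 min gives 4.59 × 0.4204 = 1.9, the same as a 2-min bed at injection. A 2-min bed at 30 min gives 1.93 × 0.3536 = 0.7. This is physical decay only; uptake, washout and motion are not modelled.

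**The case against.** The strongest reply is that 3.4 contains more than completion. Accuracy of PET/MR is listed under the feasibility objective, blinded readers report on each modality, and unreadable scans should lower the accuracy reported. It is therefore too strong to say that the plan cannot detect technical failure. That stands. What remains is that accuracy is descriptive, has no target and no rule for non-diagnostic scans, and so cannot separate technical failure from poor diagnostic performance.

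Second, a reader might infer from 6-7% residual activity at 75-80 minutes that the focused PET will be count-poor. The documents do not support this. That figure is an instantaneous end value from the longest stated session; counts summed over Part 2 may be adequate.

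Third, image quality is partly protected beforehand. Section 4.2 excludes hip arthroplasty and subjects who cannot tolerate MRI, 3.3 includes an anti-peristaltic, and an early pelvic PET exists from Part 1. So one should not infer that the protocol ignores image quality in its own scan. These measures lower the risk; they do not record the outcome.

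Fourth, no study-level success criterion exists, so a declaration of feasibility is an inference. Completion is also a legitimate descriptive measure in a pilot of 20. Both are fair. The point is only that a session with an unusable focused PET meets the patient-level endpoint.

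Finally, 3.3 says scores go into REDCap and points to Figure 2, which is not shown. An image-quality score there would answer part of the concern.

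**Conclusion.** The point holds as a gap in endpoint definition. Patient-level feasibility is completion, completion is pushed towards 100% by replacement and the completers-only population, and no visible text records whether the hybrid images were usable or says how a non-diagnostic scan enters the accuracy analysis.

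The share of non-diagnostic scans is unknown. The illustrated difference, 100% against 75% with 5 of 20 unreadable, rests on an assumed count. It shows what the endpoint would miss and does not forecast failure. The conclusion assumes that Figure 2 contains no readability score. The change is worth making before results are reported, but the study can run without it.

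Two inconsistencies met on the way need reconciling: the replacement target of 10 in 4.4 against 20 in 3.2 and 7.1, and the session times in 3.3, Figure 1 and 6.2.

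**What to change.** In 3.4, define per-subject feasibility as Part 1 and Part 2 completed in the single session and torso PET/MR, focused pelvic PET/MR and pelvic mpMRI each rated diagnostic (yes/no). The two readers already named in 3.3 give the ratings, in the existing REDCap file, before any reference result is seen. They should agree a one-line definition of diagnostic before the first reading.

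Report this rate over all subjects who start the scan, with each component's diagnostic rate beside it. Section 4.4.2 already retains data from withdrawn subjects, so this needs no new collection. In 7.2, state that non-diagnostic components are flagged in the accuracy results and not silently scored negative. If Figure 2 already includes a quality score, refer to it in 3.4 instead of adding fields.

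The cost is a few sentences in 3.4 and 7.2 and three form fields, with the same scans, readers and subjects. The drawback is a feasibility rate that may be lower than plain completion.

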4.4 Early Withdrawal of Subject

If a subject cannot finish the PET/MR imaging due to claustrophobia, he will be withdrawn. After PET/MR imaging, if a subject declines to undergo clinical evaluation and standard care of imaging, he will be withdrawn.

We plan to recruit a replacement subject in the event that a subject withdraws early to maintain the target number of 10 subjects.

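### The primary endpoint in section 3.4 does not isolate completion of the hybrid PET/MR session, so a successful session can be lost from the feasibility figure

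*Combined protocol and SAP*

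**What the plan says.** Section 2 states the primary objective: "Test whether a hybrid combination of focused C-11 choline PET/MR and pelvic mpMRI on a PET/MR system is feasible". Section 3.3 describes that combination as two parts, the torso PET/MR and the hybrid focused pelvic PET/MR with mpMRI, done in one session on the same table.

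Section 3.4 gives the patient-level primary endpoint as "Completion of all imaging examinations with laboratory results". It does not define the imaging or the laboratory results meant, and it does not mention the session or its two parts. The analysis it attaches to Objective 1 is diagnostic accuracy: "With biopsy and/or surgical histopathology as gold standard, the sensitivity, specificity and accuracy of PET/MR will be calculated".

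Other sections bear on what completion could mean:

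- Section 4.1 admits men who need clinical pelvic mpMRI, CT and bone scan. Section 4.2 excludes men who refuse them and adds "Research C-11 choline PET/MR will not substitute pelvic mpMRI, CT, or bone scan in this study". Table 1 lists all three as clinical imaging.
- These tests are partly outside the study's control. Section 4.2 says "CT and bone scan may be done elsewhere outside of Mayo Clinic", and section 6 recruits "Patients who have completed or will complete diagnostic body CT scan and nuclear medicine bone scan".
- Section 4.4 has two withdrawal rules. One concerns the scanner: "If a subject cannot finish the PET/MR imaging due to claustrophobia, he will be withdrawn". The other concerns routine care: "After PET/MR imaging, if a subject declines to undergo clinical evaluation and standard care of imaging, he will be withdrawn". Men who withdraw early are to be replaced.
- Section 7.3 analyses only men who completed every study procedure and follow-up.
- The Schedule of Events (section 6.4) lists only two imaging items, the torso PET/MR and the pelvic mpMRI, both on Day 1, and one laboratory item, the Day 0 eGFR.

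**The concern.** A feasibility endpoint should count the thing whose feasibility is in question. Here that is whether a man can get through both parts of the hybrid session. The endpoint in section 3.4 is wider than that, or at best unclear about it. Two analysts could score the same man differently: one who finishes both parts but never has a bone scan is a completer on one reading and not on the other.

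If routine imaging counts, the endpoint also reflects compliance with standard care, and it depends on how many men arrive with CT and bone scan already done. Neither says anything about the scanner session. The withdrawal rule then removes a man with a successful session for a reason unrelated to it. At stake is whether the study can give an interpretable answer to its one primary question.

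**Working it through.** **No stated figure to reproduce.** The documents give no expected completion rate and no feasibility threshold. The only computed design figure, 82% power in section 7.1, concerns a lymph-node accuracy comparison and has no bearing here. The check is therefore a comparison of passages, followed by an illustration under assumed counts.

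**Step 1: two readings of the endpoint.**

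| | Broad reading | Narrow reading |
|---|---|---|
| Imaging counted | Hybrid session plus CT and bone scan | Torso PET/MR and pelvic mpMRI only |
| Support | 4.1, 4.2, Table 1, second withdrawal rule in 4.4 | Schedule of Events, 6.4 |
| Laboratory results | Undefined | Day 0 eGFR is the only scheduled item |
| Is session completion necessary? | Yes | Yes |

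The narrow reading has a gap of its own. Section 4.2 says the research scan does not replace the clinical pelvic mpMRI, yet the Schedule of Events labels the Day 1 mpMRI as standard of care. Which mpMRI counts is not settled.

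**Step 2: follow two men through the rules.** Man A completes Parts 1 and 2, then declines the bone scan. Man B cannot finish the scan. Section 4.4 withdraws both and replaces both, and section 7.3 leaves both out of the analysis. The session succeeded for A and failed for B, but neither appears in the figure.

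**Step 3: put numbers on it.** The target is taken as 20 completers (section 3.2). The numbers starting are assumptions. Intervals are exact (Clopper-Pearson) 95%: for k of n, the lower limit is the 0.025 quantile of Beta(k, n−k+1) and the upper limit is the 0.975 quantile of Beta(k+1, n−k). When k = n the lower limit is 0.025^(1/n), so 0.025^(1/20) = 83.2% and 0.025^(1/22) = 84.6%.

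| Assumed course | Session completion, all starters | Broad endpoint, all starters | Figure under 4.4 and 7.3 |
|---|---|---|---|
| 22 start and finish the session; 2 decline routine imaging | 22/22 = 100% (84.6–100%) | 20/22 = 90.9% (70.8–98.9%) | 20/20 = 100% (83.2–100%) |
| 22 start; 2 cannot finish the session | 20/22 = 90.9% (70.8–98.9%) | 20/22 = 90.9% (70.8–98.9%) | 20/20 = 100% (83.2–100%) |
| 25 start; 5 cannot finish the session | 20/25 = 80.0% (59.3–93.2%) | 20/25 = 80.0% (59.3–93.2%) | 20/20 = 100% (83.2–100%) |

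The plan's figure is the same in all three rows. Restoring the denominator alone does not separate the first two rows. Only session completion among all starters does.

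**Step 4: the composite over all starters.** If routine imaging counts and is independent of the session (an assumption), the endpoint rate is the product of the two completion rates. With 95% session completion and 100%, 95%, 90% or 80% completion of the rest, it is 0.95 × 1.00 = 95.0%, 0.95 × 0.95 = 90.25%, 0.95 × 0.90 = 85.5% or 0.95 × 0.80 = 76.0%. Session performance is identical in all four cases.

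**The case against.** The strongest reply is that section 3.4 names neither CT nor bone scan, and that the Schedule of Events, which sets out what the study itself does, lists only the two components of the hybrid session. On that reading the endpoint is close to what the objective needs. This stands as far as it goes: the text is ambiguous, and a reader who infers that CT and bone scan are definitely part of the endpoint goes beyond it. But the ambiguity is itself the defect, and section 4.4 treats a man without standard-care imaging as not having completed.

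A reader might also infer that the endpoint does not measure feasibility at all. The documents do not support that. Session completion is necessary on either reading, and section 7.2 plans to describe procedure time, tolerance and satisfaction. Those are session-level measures, but none is a completion proportion and none has a criterion.

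A third tempting inference is that each man who skips a bone scan lowers the reported figure by 1/20, or 5 percentage points. Under the plan's rules it would not fall: he is withdrawn, replaced and left out of the analysis. The problem is that his session disappears.

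Nor is a missing laboratory result a likely cause of failure. Section 3.3 requires the eGFR before any contrast-enhanced scan, so a man who completes the contrast session already has it, barring a deviation. If another result is meant, section 3.4 does not say which.

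Finally, few men may be affected, because refusal of routine imaging is an exclusion, and imaging done before consent cannot cause a failure. Both points limit the likely size.

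**Conclusion.** The concern holds in this form: the primary endpoint does not isolate completion of the hybrid session, its imaging component is undefined, and the withdrawal rule removes some successful sessions from the feasibility figure.

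The size cannot be fixed from the documents, which give no completion or refusal rates. Under the assumed counts, true session completion could be 100%, 90.9% or 80.0% while the reported figure stays at 20/20. That rests on two premises: withdrawn men are replaced until twenty complete, and any completion figure is computed on the section 7.3 population. The plan does not actually say that a completion proportion will be reported.

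This should be changed, but it does not undermine the study. The pilot is descriptive on feasibility and sets no threshold, so no decision in the plan turns on the figure. It does bear on whether the primary question can be answered.

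**What to change.** In section 3.4:

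- Define feasibility as completion of Part 1 (torso PET/MR) and Part 2 (focused pelvic PET/MR with mpMRI) in one PET/MR session. State whether the Day 1 mpMRI is the one that counts.
- Take the proportion over all men who start the session, including those later withdrawn or replaced, and say what counts as starting. Count men who start and do not finish as failures. Report an exact 95% confidence interval. Without this denominator the new definition would also give 100% by construction, so section 7.3 needs an exception for this endpoint.
- Report availability of CT, bone scan, laboratory and pathology results separately, as data completeness for the secondary objectives.

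The replacement rule in section 4.4 refers to a target of 10 subjects, while sections 3.2 and 7.1 use 20. These should be reconciled in the same edit.

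The cost is a sentence or two in sections 3.4 and 7.3 and one more line in the results tables. No new data are needed, since section 4.4.2 already keeps data from withdrawn men. The downside is two completion figures instead of one, and a feasibility figure that may fall below 100%.

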7.1 Sample Size Determination

Our null hypothesis is the hybrid C11-choline PET/MR and pelvic multiparametric MRI will have an equal accuracy of detecting patients with malignant lymph nodes in the very high risk/high risk prostate cancer patients compared to that in the conventional CT and bone scan method. With 20 patients, a McNemar's test with a 0.05 two-sided significance level will have 82% power to reject the null hypothesis if the difference in accuracy of the two methods is 0.3 or greater and assume discordant pairs is expected to be 0.31.

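### The primary feasibility endpoint is completion, but the plan assigns it an accuracy analysis and analyses completers only, so completion is 100% by construction

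*Combined protocol and SAP*

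**What the plan says.** - **Objectives (Section 2).** The primary objective is "Test whether a hybrid combination of focused C-11 choline PET/MR and pelvic mpMRI on a PET/MR system is feasible". There are two secondary objectives. One is the added value of the hybrid examination against clinical findings. The other is the added value of "a torso C-11 choline PET/MR in comparison with conventional CT and bone scan in depicting metastasis to lymph node and bone".
- **Primary endpoint (3.4).** At patient level: "Patient: Completion of all imaging examinations with laboratory results". The data-analysis entry beneath it reads "Objective 1: Descriptive study", followed by "With biopsy and/or surgical histopathology as gold standard, the sensitivity, specificity and accuracy of PET/MR will be calculated".
- **Secondary endpoints (3.5).** NONE.
- **Sample size (7.1).** The null hypothesis is "equal accuracy of detecting patients with malignant lymph nodes in the very high risk/high risk prostate cancer patients", for hybrid PET/MR plus pelvic mpMRI against CT and bone scan. The calculation uses 20 patients, McNemar's test at two-sided 0.05, a difference of 0.3 and discordant pairs of 0.31, and states 82% power.
- **Methods (7.2).** "Descriptive statistics will be used to describe the average time of the total procedure", together with tolerance and satisfaction. The rest compares lesion counts, SUV and diagnostic accuracy between methods.
- **Withdrawal and analysis set (3.2, 4.4, 7.3).** Twenty subjects are to complete, and more may be screened to reach that number. A subject who cannot finish PET/MR because of claustrophobia, or who afterwards declines the standard imaging, is withdrawn, and withdrawals are replaced. The only analysis population defined is subjects who finished every study procedure and the follow-up.

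**The concern.** Accuracy against histology does not measure feasibility. An examination can be completed by everyone and be inaccurate, or be accurate in the few who get through it. The declared primary endpoint fits the objective, but the analysis attached to it does not, and no other section plans a completion proportion, a denominator, an interval or a criterion.

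The withdrawal and population rules make this more than a labelling slip. The subjects who show that the session was not feasible are the ones replaced and left out. A pilot meant to tell others whether a session of well over an hour on a PET/MR table can be completed would have no result capable of saying that it could not. A reader would also have trouble telling which result answers the main question, because the only powered comparison belongs to a different objective and 3.5 lists nothing.

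**Working it through.** **1. The stated power, and what it belongs to.** Inputs from 7.1: n = 20, difference d = 0.30, discordant proportion ψ = 0.31, z = 1.96. The Miettinen approximation for McNemar's test is

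power = Φ[(d√(nψ) − zψ) / √(ψ² − d²(3 + ψ)/4)]

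- d√(nψ) = 0.30 × √6.2 = 0.747
- zψ = 1.96 × 0.31 = 0.608
- denominator: √(0.0961 − 0.09 × 3.31/4) = √0.0216 = 0.147
- power = Φ(0.139/0.147) ≈ Φ(0.948) = 0.828

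This reproduces the stated 82% to within a point. The figure concerns a paired comparison of nodal accuracy. Nothing in 7.1 addresses how precisely 20 subjects estimate completion.

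**2. Tracing the completion endpoint through the plan.**

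| Section | What it contributes to completion |
|---|---|
| 3.4 | Names it as the primary endpoint, then assigns an accuracy analysis |
| 7.2 | Time, tolerance and satisfaction; no completion proportion |
| 4.4 | Non-completers withdrawn and replaced |
| 7.3 | Only completers analysed |

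Let n be the number who start and 20 the number who complete. The analysis set holds the 20 completers, so completion within it is 20/20 = 100% for every n. If the true completion rate were 80% (an assumption), about 20/0.80 = 25 starters would be expected, and the analysis set would still show 20/20.

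**3. What the endpoint would show over all starters.** The Clopper-Pearson 95% interval for x of n has lower limit equal to the 0.025 quantile of Beta(x, n − x + 1) and upper limit equal to the 0.975 quantile of Beta(x + 1, n − x), or 1 when x = n. For 20/20 the lower limit is 0.025^(1/20) = 0.832. The numbers starting are assumptions.

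| Started | Completed | Completion over starters (95% CI) | In the 7.3 set |
|---|---|---|---|
| 20 | 20 | 100% (83.2 to 100%) | 20/20 |
| 21 | 20 | 95.2% (76.2 to 99.9%) | 20/20 |
| 22 | 20 | 90.9% (70.8 to 98.9%) | 20/20 |
| 25 | 20 | 80.0% (59.3 to 93.2%) | 20/20 |

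Because recruitment stops at 20 completers, n is not strictly fixed. The lower limit is the same under that sampling scheme, and the upper limit would be slightly lower when n exceeds 20.

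Section 4.4 gives 10 as the number to be maintained by replacement, against twenty in 3.2. I used twenty, which matches 7.1. The two passages need reconciling.

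**4. Objectives against endpoints.** Section 2 has two secondary objectives and 3.5 has no endpoint for either, while the accuracy measures that would serve them sit in 3.4 under Objective 1. The 7.1 hypothesis shares its comparator and nodal target with secondary objective 2. The match is not exact: 7.1 names hybrid PET/MR plus mpMRI and covers nodes only, whereas the objective names torso PET/MR and covers nodes and bone.

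**The case against.** Feasibility is not left to accuracy alone. Section 7.2 opens with procedure time, tolerance and satisfaction, which are reasonable feasibility measures in a pilot of 20. Section 4.4.2 retains the data of withdrawn subjects, so a completion count could be taken from the records without any amendment. This stands, and it rules out saying that feasibility goes unanalysed or that the information is lost. It does not supply the missing analysis. None of the three measures is the 3.4 endpoint, and under 7.3 they too would come from completers, who are likely to be the subjects who tolerated the session best.

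A reader might also infer that the powered comparison has no outcome in the plan. The documents do not support that. Section 7.1 gives the unit, the condition, the comparator and the test; 7.2 lists the accuracy measures for both methods; and Table 1 sets out imaging and reference standard by region. What is missing is the entry under 3.5 and a statement of which objective the calculation serves. It would likewise be too strong to call 7.1 the sample size for secondary objective 2, given the mismatch shown in the working.

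Nor does this point dispute the 82%. Other versions of the test give other values (57% for the exact two-sided test), but that is a separate question.

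**Conclusion.** The concern holds in this form: the declared primary endpoint has no matching analysis, and under 4.4 and 7.3 taken together it equals 100% in the only analysis set, so it cannot show infeasibility. The intervals in the working give the scale. Even if nobody fails, 20 subjects support a lower limit of only 83.2%. With 25 starters the true picture would be 80.0% (59.3 to 93.2%), while the analysis set still reads 20/20.

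The conclusion rests on reading 7.3 as governing every analysis, since it is the only population defined, and on twenty as the completion target. The numbers of starters are illustrations, not forecasts. The secondary part, that 3.5 conflicts with Section 2 and that 7.1 does not say which objective it serves, is a matter of structure and has no numerical effect of its own.

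**What to change.** 1. **3.4 and 7.2.** Make the Objective 1 analysis the number meeting the completion endpoint as 3.4 already states it, divided by all subjects who started the PET/MR session, including those later withdrawn or replaced, with an exact 95% CI. Say what counts as starting; being positioned on the scanner table would serve, since the tracer is injected there. Report completion of the PET/MR session separately from completion of the standard-of-care imaging, because 4.4 withdraws subjects for failing either and the two say different things about feasibility.
2. **7.3.** Exempt this analysis, and the time and tolerance summaries, from the completers-only rule. Without this change, item 1 would contradict 7.3.
3. **3.5.** Replace NONE with the accuracy measures now in 3.4, mapped to the two secondary objectives.
4. **7.1.** State that the McNemar calculation supports a secondary comparison of nodal accuracy, and reconcile the method it names with the torso PET/MR of secondary objective 2. Add the precision that about 20 subjects give for completion.

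The cost is protocol wording and a log of everyone who starts; no further subjects or procedures are needed. The downside for the sponsor is that the feasibility figure may fall below 100% and the powered comparison becomes visibly secondary.
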